#### **6.4. Study Intervention Compliance**

All Site personnel involved with the receipt, storage, preparation, administration, and destruction of study drug are required to document their understanding of the Study Drug Injection Guidelines. Refer to the Injection Guidelines.

All study drug will be administered under the supervision of the Investigator.

Compliance with study drug administration instructions will be assessed through the review of accountability and preparation logs as well as the reconciliation of used and unused vials, vials destroyed, and vials returned to the Sponsor.

#### **6.5. Concomitant Therapy**

Standard of care for ALS is presented in the American Academy of Neurology (AAN) guideline regarding management and care of the patient with ALS. Recommendations are presented for multidisciplinary care, symptom management, and the treatment of cognitive/ behavioral impairment.

#### **6.6. Dose Interruption**

No intentional modifications of the number or concentration of doses will be permitted. An unintentional interruption of the number of injections (128 per Study Injection Visit) is only allowed if the Participant experiences an AE related to study drug administration or other health-related events (e.g., illness) during the study. If the full set of study injections cannot be administered during the normal Study Injection Visit, the Participant should be scheduled to receive the remaining injections within 48 hours. If this is not possible, then the remainder of the injections for that visit will not be administered.

#### **6.7. Prior and Concomitant Medications, Treatments, and Procedures**

Medications and treatments taken within 30 days prior to Day 0 will be recorded on the Medication and History eCRF at the Day 0 Visit. Any medication or vaccine, including over-the-counter or prescription medicines, vitamins, herbal supplements, and topical anesthetics for post-injection pain and procedures that the Participant is receiving at the time of enrollment or receives during the study must be recorded on the Concomitant Medications or Concomitant Procedures eCRF. For each medication or treatment, the following information will be collected:

- Medication trade or generic name, or procedure
- Indication for which the medication/procedure was given

- Dose/strength, route, and frequency of administration
- Date started and date stopped (or continuation at study exit)
- Reason for use

The medical monitor will be contacted if there are any questions regarding concomitant or prior therapy.

---

## 7. DISCONTINUATION OF STUDY INTERVENTION AND PARTICIPANT WITHDRAWAL

### 7.1. Discontinuation of Study Intervention

In rare instances, it may be necessary to discontinue study drug for a Participant. If study drug is discontinued, the Participant will remain in the study to be evaluated for safety if the Participant agrees to continue participating in the study. See Section 1.3 (SoA) for any further assessments that need to be completed.

### 7.2. Participant Withdrawal/Discontinuation

Any Participant may voluntarily discontinue the study at any time without prejudice. The Investigator may discontinue a Participant from the study at any time if, in the Investigator's judgment, the Participant's health or safety would be compromised by remaining in the study.

Specific reasons for study discontinuation include the following:

- Participant decision
- Investigator's decision
- Adverse event
- Insufficient compliance with study requirements
- Lost to follow-up
- Other

The specific reasons for Participant discontinuation will be recorded.

The following assessments will be performed at an Early Termination (ET) Visit, if possible, for Participants who discontinue prior to the Day 180 Visit.

- Complete Physical examination
- Vital signs, weight
- 12-lead ECG
- Serum chemistry and hematology
- Urine pregnancy test
- SVC
- Concomitant medications
- Muscle strength by HHD
- ATLIS (where available)
- ALSFRS-R
- ALSAQ-40
- PGIC and CGIC
- Injection site reaction assessment if discontinued prior to Day 144
- Treatment-emergent adverse events

---

**7.3. Lost to Follow-up**

A Participant will be considered lost to follow-up if he or she repeatedly fails to return for scheduled Visits and is unable to be contacted by the Site by Day 180 (+7 days).

The following actions must be taken and recorded if a Participant fails to return to the clinic for a required study Visit:

- The site must attempt to contact the Participant and reschedule the missed Visit as soon as possible. The site must counsel the Participant on the importance of maintaining the assigned Visit schedule and ascertain whether or not the Participant wishes to and/or should continue in the study.
- If no response is obtained from the Participant, the Investigator is encouraged to contact one of the Participant's relatives or his/her general practitioner.
- Before a Participant is deemed lost to follow up, the Investigator or designee must make every effort to regain contact with the Participant, including at least three telephone calls and, finally, a certified letter to the Participant's last known mailing address. These contact attempts should be documented in the source records.
- Should the Participant continue to be unreachable, the Participant will be considered lost to follow-up.

---

## 8. STUDY ASSESSMENTS AND PROCEDURES

All study procedures and assessments together with their timing are summarized in Section 1.3 (SoA).

Protocol waivers or exemptions are not allowed. Adherence to the protocol requirements is essential.

### 8.1. Screening (Days -30 to -1)

#### 8.1.1. Screening Procedures

During Screening, and prior to randomization, Participant eligibility will be assessed, and the following Screening procedures will be conducted:

- Informed consent prior to any study-related procedures
- Evaluation of eligibility criteria
- Diagnosis confirmed for clinically definite or probable ALS or laboratory supported probable ALS as defined in the revised El Escorial/Airlie House diagnostic criteria
- Demographics, baseline characteristics, and medical history
- Concomitant medications and procedures
- ALSFRS-R
- SVC
- Vital signs, weight, and height
- Complete physical examination
- 12-Lead ECG
- Serum chemistry and hematology, and coagulation profile
- Urine Pregnancy Test (for women of childbearing potential only)
- Viral Screening – HIV, Anti-Human T-Cell Lymphotropic Virus (HTLV) I/II antibody with reflex confirmatory assay, Hepatitis B core antibody (IgM HBcAb), antibody to Hepatitis B antigen (HBsAb), Hepatitis B surface antigen (HBsAg) in addition to a quantitative HBV viral load if needed clinically, and Hepatitis C antibodies (Anti-HCV) and a positive qualitative PCR to assess HCV viral load

#### 8.1.2. Revised El Escorial/Airlie House Criteria

According to the Revised El Escorial/Airlie House guidelines, definitions for ALS are as follows:

- **Clinically definite ALS** is defined by clinical or electrophysiological evidence by the presence of lower motor neuron (LMN) as well as upper motor neuron (UMN) signs in

---

the bulbar region and at least 2 spinal regions or the presence of LMN and UMN signs in 3 spinal regions.

- **Clinically probable ALS** is defined on clinical or electrophysiological evidence by LMN and UMN signs in at least 2 regions with some UMN signs necessarily rostral to (above) the LMN signs.
- **Probable ALS–Laboratory Supported**, which is defined when clinical signs of UMN and LMN dysfunction are found in only 1 region but electrophysiological signs of LMN loss are observed in ≥2 regions.

## 8.2. Safety Assessments

### 8.2.1. Physical Examinations

A complete physical examination (PE) will be performed at the Screening, predose on Days 0, 14, 60, 74, 120, and 134, and on Days 30, 84, 144, and Day 180/ET. The complete PE will include the following: an examination of the skin/integumentary systems, general appearance, head, neck (including thyroid), eyes, ears, nose, throat, lymph nodes, chest (lungs), heart, abdomen, musculoskeletal system, neurological system, and any additional assessments needed to establish Baseline status or evaluate symptoms or AEs. Height will be recorded only during Screening. Any abnormalities should be categorized as clinically significant (CS) or not clinically significant (NCS), and the abnormalities recorded.

The Investigator or qualified medical personnel who routinely perform these evaluations in patients with ALS will conduct the examination, determine findings, and assess any abnormalities as to clinical significance.

### 8.2.2. Medical History

A detailed description of the Participant's current disease status, past medical conditions (including cancer), social history, and medication and treatment history will be recorded at the Screening Visit.

The Investigator will confirm the diagnosis of ALS using the revised El Escorial / Airlie House diagnostic criteria.

Social history includes familial, occupational, and recreational aspects of the Participant's personal life that have the potential to be clinically significant, including caffeine, nicotine, alcohol, and illicit drug use.

Medication and treatment history will also be collected at Screening, including riluzole and edaravone.

Cancer history will be collected for the 3 years prior to Screening. Familial cancer history will also be collected.

---

Any untoward medical events that occur from the time of consent and during the Screening period (prior to study drug administration) will be captured as AEs in the electronic case report form (eCRF). A change in medical status or medical history from time of signing of informed consent through first dose of study drug is to be reported as an AE or SAE (only if associated with a study specific procedure) as appropriate.

### **8.2.3. 12-Lead Electrocardiograms**

12-Lead ECGs will be performed during Screening, Day 84, and Day 180/ET. Any clinically significant abnormalities are to be recorded. The ECG recording will be printed out and stored with the Participant's records.

### **8.2.4. Vital Signs**

Vital signs will be measured at Screening and all subsequent study visits, including pre- and post-dose at Study Injection Visits during Treatment Cycle 1 (Days 0 and 14), Treatment Cycle 2 (Days 60 and 74), and Treatment Cycle 3 (Days 120 and 134), and at all other Study Visits (Days 30, 84, 144, and 180/ET). Weight will be collected predose at Study Injection Visits. After resting in the seated position for 5 minutes, vital signs will be recorded including temperature, sitting blood pressure, heart rate, respiratory rate, and oxygen saturation on room air. The method of temperature measurement should be according to the Site's policy and should be consistently applied.

### **8.2.5. Coagulation Profile**

Blood samples for measurement of coagulation profile parameters (PT, PTT, and INR) will be collected at Screening.

### **8.2.6. Clinical Laboratory Assessments**

The Investigator must review the laboratory report, document this review, and record any clinically relevant changes occurring during the study. The laboratory reports must be filed with the source documents. Clinically significant abnormal laboratory findings are those that are not associated with the underlying disease, unless judged by the Investigator to be more severe than expected for the Participant's condition.

All protocol-required laboratory assessments must be performed in accordance with the laboratory manual and the SoA.

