#### 9.3.1. Primary Endpoints

Safety analyses in this study will evaluate the safety profile of Engensis as compared with Placebo. The primary endpoints for safety are as follows:

- Incidence of TEAEs and TESAEs for Engensis compared to Placebo
- Incidence of injection site reactions for Engensis compared to Placebo
- Incidence of clinically significant laboratory values for Engensis compared to Placebo

No formal statistical testing will be conducted for the safety analyses. All Participants in the safety subset will be included in these analyses. Participants will be grouped by treatment received. All summaries will be derived based on available data. No imputation will be performed for missing values. All safety analyses will be made on the Safety Population.

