**Events Meeting the AE Definition**

- Any abnormal laboratory test results (hematology, or clinical chemistry) or other safety assessments (e.g., ECG, radiological scans, vital signs measurements), including those that worsen from Baseline, considered clinically significant in the medical and scientific judgment of the investigator (i.e., not related to progression of underlying disease).
- Exacerbation of a chronic or intermittent pre-existing condition including either an increase in frequency and/or intensity of the condition.
- New conditions detected or diagnosed after study intervention administration even though it may have been present before the start of the study.
- Signs, symptoms, or the clinical sequelae of a suspected drug-drug interaction.
- Signs, symptoms, or the clinical sequelae of a suspected overdose of either study intervention or a concomitant medication. Overdose per se will not be reported as an AE/SAE unless it is an intentional overdose taken with possible suicidal/self-harming intent. Such overdoses should be reported regardless of sequelae.

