**Events NOT Meeting the AE Definition**

- Any clinically significant abnormal laboratory findings or other abnormal safety assessments that are associated with the underlying disease, unless judged by the Investigator to be more severe than expected for the Participant's condition.
- The disease/disorder being studied or expected progression, signs, or symptoms of the disease/disorder being studied, unless more severe than expected for the Participant's condition.
- Medical or surgical procedure (e.g., endoscopy, appendectomy): the condition that leads to the procedure is the AE.
- Situations in which an untoward medical occurrence did not occur (social and/or convenience admission to a hospital).

- Anticipated day-to-day fluctuations of pre-existing disease(s) or condition(s) present or detected at the start of the study that do not worsen.

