#### Assessment of Causality

- The Investigator is obligated to assess the relationship between study intervention and each occurrence of each AE/SAE.
- A “reasonable possibility” of a relationship conveys that there are facts, evidence, and/or arguments to suggest a causal relationship, rather than that a relationship cannot be ruled out.
- The Investigator will use clinical judgment to determine the relationship.
- Alternative causes, such as underlying disease(s), concomitant therapy, and other risk factors, as well as the temporal relationship of the event to study intervention administration will be considered and investigated.
- The Investigator will also consult the IB and/or Product Information, for marketed products, in his/her assessment.
- For each AE/SAE, the Investigator **must** document in the medical notes that he/she has reviewed the AE/SAE and has provided an assessment of causality.

- Situations may arise in which an SAE has occurred, and the Investigator has minimal information to include in the initial report to the Sponsor or designee. However, the Investigator must always assess causality for every event before the initial transmission of the SAE data to the Sponsor or designee. Death or hospitalization are not to be specified as an SAE; these are criteria to determine seriousness.
- The Investigator may change his/her opinion of causality in light of follow-up information and send an SAE follow-up report with the updated causality assessment.
- The causality assessment is one of the criteria used when determining regulatory reporting requirements.

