6.2 Derived Data

This section describes the derivations required for statistical analysis. Unless otherwise stated, variables derived in the source data will not be re-calculated.

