Measured values of serum chemistry and hematology analyses and their changes from baseline, will be presented with descriptive statistics at each visit by treatment group (Tables 14.3.4.1 and 14.3.4.3). Incidence of clinically significant values and shift tables by the clinical significance based on laboratory assessments will be presented for each parameter (Tables 14.3.1.9, 14.3.4.2, 14.3.4.4). Percentages for each parameter will be based on the number of participants who have at least one measurement for at baseline and at corresponding post-baseline visit.

Result of urine pregnancy test is variable with two possible values: positive / negative. The test should be performed only for women with childbearing potential at Screening, Day 0 pre-dose and End of Study. Urinalysis will be presented only in a listing.

Results of serum chemistry, hematology and urine pregnancy tests will be listed (Listings 16.2.8.1 – 16.2.8.3).

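### The laboratory primary endpoint counts a value as clinically significant partly on whether it is attributed to ALS, and the protocol uses that term inconsistently

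*Protocol*

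**What the plan says.** The third primary endpoint (Protocol 9.3.1, SAP 3.1) is "Incidence of clinically significant laboratory values for Engensis compared to Placebo". The rule for the term is in Protocol 8.2.6 and again in 8.2.6.1: "Clinically significant abnormal laboratory findings are those that are not associated with the underlying disease". The same sentence goes on: "unless judged by the Investigator to be more severe than expected for the Participant's condition".

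Three other places bear on the term:

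- Protocol 10.2.1, events that meet the AE definition, covers abnormal results "considered clinically significant in the medical and scientific judgment of the investigator (i.e., not related to progression of underlying disease". This agrees with 8.2.6 but leaves out the exception.
- Protocol 10.2.1, events that do not meet the AE definition, begins "Any clinically significant abnormal laboratory findings or other abnormal safety assessments that are associated with the underlying disease". Here a finding can be clinically significant and disease-associated at once.
- Protocol 8.5.9 says that disease-related events qualify as AEs or SAEs, apart from a short list of ALS signs and symptoms (numbness, pain, tingling or burning, cramps, sensitivity to touch).

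SAP 6.14.2 plans: "Incidence of clinically significant values and shift tables by the clinical significance based on laboratory assessments will be presented for each parameter" (Tables 14.3.1.9, 14.3.4.2 and 14.3.4.4). It gives no definition, threshold or grade of its own, and SAP 9 reports no change from the protocol. SAP 6.14.2 also tabulates measured values and changes from baseline by visit and arm (Tables 14.3.4.1 and 14.3.4.3) and lists all results.

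**The concern.** In a placebo-controlled trial, the comparison of arms shows whether abnormalities are due to treatment or to disease. Here part of that question is settled case by case before the event is counted. A treatment-caused abnormality that looks like ALS, and does not look unusually severe, is not an event for a primary endpoint and does not appear as clinically significant in the shift tables.

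The exception reduces the problem but is itself a judgment against expected ALS, with no criterion given. Because 8.2.6 and 10.2.1 use the term in two senses, two sites can follow the protocol faithfully and flag the same value differently. No planned table counts participants with out-of-range values, so nothing of the same kind exists to set beside the flag.

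**Working it through.** **Step 1. One value under each section.** Take an abnormal result that the Investigator regards as medically important, attributes to ALS, and does not find worse than expected.

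| Section | Clinically significant? | An AE? |
|---|---|---|
| Protocol 8.2.6, 8.2.6.1 | No | Not addressed |
| Protocol 10.2.1, meets AE definition | No, by its gloss on the term | No, under this item |
| Protocol 10.2.1, does not meet AE definition | Can be yes | No |
| Protocol 8.5.9 | Not addressed | Yes, if it counts as a disease-related event outside the listed symptoms |

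The flag, and whether the value is an AE, depend on which section the site follows. Causality is recorded for AEs ("The Investigator is obligated to assess the relationship between study intervention and each occurrence of each AE/SAE", Protocol 10.2.5). Where 10.2.1 keeps the value from being an AE, that assessment is not triggered and the attribution need not be recorded anywhere.

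**Step 2. Effect on the comparison.** The documents give no event rate, power or precision for this endpoint, so there is no stated figure to reproduce. The allocation is 18 at 2:1: 18 × 2/3 = 12 Engensis and 18 × 1/3 = 6 Placebo.

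Define:

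- p_E, p_P: true proportions with a medically important abnormality in each arm.
- a: share of these attributed to ALS; r: share of those readmitted by the exception.
- s = a(1 − r): share that goes unflagged.

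The flagged proportion in each arm is p(1 − s). With s equal in both arms, the expected difference is (p_E − p_P)(1 − s). If abnormalities caused by the drug resemble ALS more than other abnormalities do, s is larger under Engensis and the loss is greater.

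**Step 3. Illustration only.** Every p and s below is an assumption. Each participant is treated as one unit, flagged or not. A definition without regard to cause corresponds to s = 0.

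Scenario A: 25% against 0%. Expected flagged = 12 × 0.25(1 − s). Chance that none of 12 is flagged = [1 − 0.25(1 − s)]^12.
Scenario B: 50% against 1/6. Expected difference = (0.5 − 1/6)(1 − s).

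| s | A: expected flagged of 12 | A: chance of none | B: expected difference |
|---|---|---|---|
| 0 | 3.0 | 3.2% | 33.3 points |
| 0.25 | 2.25 | 8.3% | 25.0 points |
| 0.5 | 1.5 | 20.1% | 16.7 points |
| 0.75 | 0.75 | 46.1% | 8.3 points |
| 1 | 0 | 100% | 0 points |

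For example, at s = 0.5 in A the flagged rate is 0.125 and 0.875^12 = 0.201. The table shows direction and scale and does not predict this trial.

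**The case against.** Several points on the other side stand.

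- **The rule is not absolute.** A reader might infer that a value counts only when it is not attributed to ALS. The exception rules that out, because some attributed values are readmitted. In the working, r covers this.
- **The data are not lost.** A reader might infer that a treatment effect could vanish from the report. It could not. Values and changes are summarised with minimum and maximum (SAP 6.3), everything is listed, and with 18 participants each value can be read by arm. Protocol 8.2.6 also asks Investigators to record clinically relevant changes, with no condition about cause. What is missing is a count of participants with excursions. Early-termination and unscheduled post-baseline values are also kept out of tables (SAP 6.2.14).
- **Injection-related enzyme rises are not the argument.** It is tempting to say that muscle enzymes raised by 128 injections per visit would be written off as ALS. Both arms receive the injections. Scheduled post-baseline draws fall on Days 60, 120 and 180, after injections on Days 14, 74 and 134, a nominal gap of 46 days each time (60 − 14, 120 − 74, 180 − 134). A short-lived rise would usually be missed under any definition, and the documents do not say which analytes ALS alters.
- **Investigators are blinded** (Protocol 6.3.2), so the known arm cannot steer attribution. Blinding does not stop dilution, because attribution follows how the abnormality looks. With equal s the ratio p_E(1 − s)/p_P(1 − s) is unchanged in expectation, but the counts and the difference still shrink, and with 12 and 6 participants the counts are already small.
- **No decision depends on it.** Safety is not formally tested (Protocol 9.3.1).

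**Conclusion.** The concern holds in this form: attribution to ALS, softened by an exception without a criterion, is part of the definition of a primary endpoint, and the protocol uses the defining term in two incompatible ways. The consequence is a possible undercount of treatment-caused abnormalities in Tables 14.3.1.9, 14.3.4.2 and 14.3.4.4, with the expected difference reduced by (1 − s) when s is equal across arms. The size cannot be determined, since the documents give neither the true rates nor the share attributed to ALS; the percentages above rest wholly on assumed inputs.

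The documents do not support the stronger conclusions that every ALS-attributed value is dropped, that the report would hide an effect, or that Investigators could favour an arm. Because the endpoint is descriptive and the underlying values are reported, this is a point that should be fixed, not one that must be fixed before the plan can be used.

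**What to change.** 1. For the laboratory endpoint, define clinical significance by medical importance irrespective of presumed cause. State this in Protocol 8.2.6 and 8.2.6.1 and in SAP 6.14.2, which now has no definition.
2. Record attribution (ALS, study drug, other) in a separate field for every flagged value, whether or not it becomes an AE.
3. Add Low/Normal/High shift and incidence tables by arm beside the tables based on the flag. Use each laboratory's own reference range, because 8.2.6.1 assigns Screening to local laboratories and later visits to the central one.
4. Reconcile 8.2.6, 8.2.6.1, 8.5.9 and the two lists in 10.2.1, so that a disease-associated laboratory finding has one status. A wholesale rewrite of the AE definition is not needed for this endpoint and would change AE collection across the trial.

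Cost: a few sentences of protocol, SAP and CRF guidance, one data field, and one extra table per panel. Local reference ranges, which Protocol 10.1.8 has sites retain, must be in the database if they are not already. More values will count as clinically significant in both arms. The judgment of medical importance will still vary between sites, which is why the reference-range tables are needed as well.
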